6.3 Recording of adverse events

6.3.1 Time period for collection of adverse events

Adverse events will be collected throughout the study, from informed consent until 30 days after the end of the last investigational product administration.

SAEs will be recorded from the time of informed consent and should be reported to Sarah Cannon Safety Department as described in Section [6.4](#).

Following discontinuation of study treatment, SAEs considered related to study procedures should continue to be collected while patients are followed-up for disease progression.

For each patient who discontinues study treatment for a reason other than disease progression:

- Follow-up information on all ongoing AEs should continue to be collected until the survival follow-up.
- SAEs considered related to study procedures must continue to be collected and reported using standard SAE timelines and process until the end of progression follow-up (i.e., disease progression).
- All deaths must continue to be collected after progression and during the survival follow-up.

6.3.2 Follow-up of unresolved adverse events

Any AEs that are unresolved at the patient's last visit in the study (after the EOT visit) are followed up by the Investigator for as long as medically indicated, but without further recording in the eCRF.

AstraZeneca retains the right to request additional information for any patient with ongoing AE(s) at the end of the study, if judged necessary.

If an Investigator learns of any SAEs, including death, at any time after a patient has completed the study and he/she considers there is a reasonable possibility that the event is related to AZD1775, the Investigator should notify Sarah Cannon.

6.3.3 Variables

The following variables will be collected for each AE;

- AE (verbatim)
- The date when the AE started and stopped
- CTCAE grade and changes in grade during the course of the AE
- Whether the AE is serious or not
- Causality rating against AZD1775 (yes or no)
- Action taken with regard to AZD1775
- Outcome

In addition, the following variables will be collected for SAEs:

- Date AE met criteria for serious AE
- Date Investigator became aware of serious AE
- Reason AE is serious
- Date of hospitalisation
- Date of discharge
- Probable cause of death
- Date of death
- Autopsy performed
- Causality assessment in relation to study procedure(s)
- Causality assessment in relation to other medication(s)
- Description of AE.

The grading scales found in the revised CTCAE Version 4.03 will be utilized for all events with an assigned CTCAE grading. For those events without assigned CTCAE grades, the recommendation in the CTCAE criteria should be utilized that converts mild, moderate, and severe events. A copy of the current CTCAE version can be downloaded from the Cancer Therapy Evaluation Program website (<http://ctep.cancer.gov>).

It is important to distinguish between serious and severe AEs. Severity is a measure of intensity whereas seriousness is defined by the criteria in Section 6.2. An AE of severe intensity need not necessarily be considered serious. For example, nausea that persists for several hours may be considered severe nausea, but not a SAE. On the other hand, a stroke that results in only a limited degree of disability may be considered a mild stroke but would be a SAE.

6.3.4 Causality collection

The Investigator will assess causal relationship between AZD1775 and each AE, and answer ‘yes’ or ‘no’ to the question ‘Do you consider that there is a reasonable possibility that the event may have been caused by the investigational product?’

For SAEs causal relationship will also be assessed for other medication and study procedures. Note that for SAEs that could be associated with any study procedure the causal relationship is implied as ‘yes’.

A guide to the interpretation of the causality question is found in [Appendix A](#) to the CSP.

6.3.5 Adverse events based on signs and symptoms

All AEs spontaneously reported by the patient, reported in response to the open question from the study personnel, or revealed by observation will be collected and recorded in the eCRF.

When collecting AEs, the recording of a diagnosis is preferred (when possible) to the recording of a list of signs and symptoms. However, if a diagnosis is known and there are other signs or symptoms that are not generally part of the diagnosis, the diagnosis and each sign or symptom will be recorded separately.

They do not include metastases of the original cancer.

6.3.6 Adverse events based on examinations and tests

The results from protocol mandated laboratory tests and vital signs will be summarised in the CSR. Deterioration as compared to baseline in protocol-mandated laboratory values, vital signs should therefore only be reported as AEs if they fulfil any of the SAE criteria or are the reason for discontinuation of treatment unless clearly due to the progression of disease under study.

If deterioration in a laboratory value/vital sign is associated with clinical signs and symptoms, the sign or symptom will be reported as an AE and the associated laboratory result/vital sign will be considered as additional information. Wherever possible the reporting Investigator uses the clinical rather than the laboratory term (e.g., anaemia versus low haemoglobin value). In the absence of clinical signs or symptoms, clinically relevant deteriorations in non-mandated parameters should be reported as AE(s).

Deterioration of a laboratory value, which is unequivocally due to disease progression, should not be reported as an AE/SAE.

Any new or aggravated clinically relevant abnormal medical finding at a physical examination as compared with the baseline assessment will be reported as an AE.

Examples of these are marked haematological and other laboratory abnormalities, and certain events that lead to intervention (other than those already classified as serious), dose reduction or significant additional treatment.

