2.2 Secondary objectives

Secondary Objective :	Outcome Measure :
To evaluate the safety and tolerability of AZD1775 monotherapy in patients with locally advanced or metastatic solid tumours.	Treatment-emergent adverse events (TEAEs) and SAEs
To evaluate the preliminary anti-tumour activity of AZD1775 monotherapy in patients with locally advanced or metastatic solid tumours.	Best objective response (OR) to treatment will be assessed by dose level cohort according to Response Evaluation Criteria in Solid Tumours (RECIST) v1.1 (Eisenhauer et al 2009).
To evaluate the PK profile of AZD1775 monotherapy in patients with locally advanced or metastatic solid tumours.	PK parameters of AZD1775
To evaluate the preliminary effect of a high-fat meal on the PK profile of AZD1775 monotherapy in patients with locally advanced or metastatic solid tumours.	PK parameters of AZD1775
To characterise the effect of AZD1775 on QTc interval in patients with locally advanced or metastatic solid tumours.	QTc interval

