6.7 Management of IP related toxicities

Toxicity will be assessed utilising the NCI CTCAE v4.03 (<http://evs.nci.nih.gov/ftp1/CTCAE/CTCAE>), unless otherwise specified.

Dose adjustments will be based on the organ system exhibiting the greatest degree of toxicity. Dose reductions or holds and initiation of supportive care are allowed as clinically indicated by the treating physician. Additional unscheduled PK samples should be collected for any AE

possibly related to AZD1775. The date and time of last study drug administration should be collected and recorded on an ‘Unscheduled PK’ sample eCRF page. The additional PK samples should not be taken if the last dose of study drug(s) was administered > 1 week prior to the event.

A maximum of 2 dose reductions for AZD1775 will be allowed. Patients requiring >2 dose reductions will be discontinued from the study drug.

There are different doses and schedules being evaluated currently. Dose should be reduced to a previous dose level for a toxicity. Patients starting at 125 mg BID can be dose reduced to 125 mg QD if needed for management of toxicity. Patients on 150 mg BID can be dose reduced to 125 mg BID and potentially 150 mg QD if needed for management of toxicity. Patients on 200 mg QD can be dose reduced to 150 mg QD and potentially 125 mg QD if needed for management of toxicity.

Any patient requiring a toxicity-related dose delay of more than 21 days from the intended day of the next scheduled dose must be discontinued from the study unless there is approval from the Medical Monitor for the patient to continue.

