6.7.2 Dose modifications due to haematologic toxicity

Complete blood counts (CBC) will be obtained for all patients at the beginning of each treatment cycle (Day 1). If haematologic toxicity occurs (see [Table 9](#)), treatment should be held and ANC and platelets should be monitored weekly until recovery.

Table 9 Cycle Day 1 Haematologic Dose Modifications

Treatment Day Blood Counts and Toxicity			
ANC		Platelets	Action
≥1000/μL	And	≥75,000/μL	No dose modification or interruption
<1000/μL	Or	<75,000/μL	Delay by 1 week intervals until recovery

If haematologic toxicity parameters do not recover within 21 days, the patient should be removed from the study treatment.

Table 10 Neutropenia, Infection, Febrile Neutropenia Dose Modifications and Management

Any Day	

Grade 3 neutropenic fever (ANC <1000/μL + Temperature \geq101°F [38.5°C]) or neutropenic infection
 
Documented infection with Grade 3 neutropenia (ANC <1000/μL)
 
Grade 4 neutropenia (ANC <500/μL >7 days)
 
Grade 4 thrombocytopenia (platelet count <25,000/μL >7 days)
	
Hold dose until recovery.
 
Then, upon resuming dosing, reduce AZD1775 to the next lower dose level^a.

Grade 4 febrile neutropenia or Grade 4 infection with neutropenia (both defined as septic shock)
 
Thrombocytopenic haemorrhage (gross occult bleeding) associated with a platelet count <50,000/μL
	
Discontinue treatment and follow for disease progression.

a No more than two dose reductions will be allowed for any patient. Patients requiring additional dose modifications due to toxicity will discontinue study treatment.

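### Section 6.3.6 contradicts itself on whether asymptomatic, non-serious laboratory deteriorations are AEs, so cytopenias that delay or reduce dosing may be recorded inconsistently in the TEAE tables

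*Protocol*

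**What the plan says.** Section 6.3.6 starts from the premise that "The results from protocol mandated laboratory tests and vital signs will be summarised in the CSR". It concludes that deteriorations in those values "should therefore only be reported as AEs if they fulfil any of the SAE criteria or are the reason for discontinuation of treatment", with a carve-out for clear disease progression. Where a laboratory change comes with clinical signs, "the sign or symptom will be reported as an AE and the associated laboratory result/vital sign will be considered as additional information". Asymptomatic changes in parameters that are not mandated are to be reported if clinically relevant.

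The section then requires new or aggravated physical-examination findings to be reported as AEs. It ends: "Examples of these are marked haematological and other laboratory abnormalities, and certain events that lead to intervention", and goes on to list dose reduction and significant additional treatment.

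Neutrophils and platelets are on the mandated list in section 5.2.1. The outcome measure for the safety and tolerability objective in section 2.2 is "Treatment-emergent adverse events (TEAEs) and SAEs", and section 8.3.4 defines a TEAE as an AE with onset in a given window.

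In section 6.7.2, Table 9 delays a cycle on blood counts alone. For Grade 4 neutropenia or thrombocytopenia lasting more than 7 days, Table 10 requires a hold and says: "Then, upon resuming dosing, reduce AZD1775 to the next lower dose level". Section 7.2.2 lists the same event among the DLT criteria.

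**The concern.** Section 1.2.3 names anaemia, neutropenia and thrombocytopenia as adverse reactions to AZD1775 monotherapy. Sections 6.7.2 and 7.2.2 treat low counts as serious enough to delay or reduce dosing or to count against a dose level. The main sentence of 6.3.6 nevertheless keeps such a count out of the AE record unless it is serious, ends treatment or comes with symptoms.

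The closing paragraph points the other way but does not settle the matter. It follows a sentence about physical-examination findings, and laboratory values cannot be examples of those. Two sites could each follow the section in good faith and record the same event differently.

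What is at stake is consistent ascertainment of a stated secondary safety outcome, reported by dose level cohort. Section 6.3.3 also makes causality and action taken variables of the AE form. An event with no AE entry carries neither, and a dose reduction may appear in the dosing record with no AE to explain it.

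**Working it through.** The plan states no figure on this point and there is nothing to recompute. The check takes each haematologic trigger through the two parts of 6.3.6 and then to the planned outputs.

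| Event | Main sentence of 6.3.6 | Closing paragraph of 6.3.6 | Captured elsewhere |
|---|---|---|---|
| Asymptomatic Day 1 ANC <1000/µL or platelets <75,000/µL: Table 9 delay | Not an AE | Delay is not named; an AE only if the count is thought marked | Laboratory summary (8.4.3); interruption summary (8.4.2) if a delay is counted there |
| Asymptomatic Grade 4 neutropenia or thrombocytopenia >7 days: Table 10 hold and reduction | Not an AE unless judged serious | AE: marked abnormality and dose reduction | Laboratory summary (8.4.3); interruptions and reductions (8.4.2) |
| The same event as a DLT (7.2.2) | Not an AE unless judged serious | AE if thought marked or dosing is reduced | 24-hour DLT report (7.2.3); DLT summary (8.4.3) |
| Neutropenic fever, neutropenic infection, thrombocytopenia with bleeding | The sign or symptom is an AE | Consistent | DLT and laboratory summaries, where they apply |
| Cytopenia that is serious or ends treatment | AE | Consistent | SAE and discontinuation summaries |

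The two parts conflict directly in row 2 and can conflict in row 3. In row 1 the main sentence excludes the event, and the closing paragraph does not expressly bring it back. Rows 4 and 5 show no loss.

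Two other places bear on the conflict:

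- Section 6.1 counts abnormal laboratory findings among possible AEs, which favours recording.
- The 6.3.6 sentence on asymptomatic changes in non-mandated parameters favours the restrictive reading of mandated ones, because it would be unnecessary if all relevant changes were AEs.

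Weight of a single event: Table 12 plans 3-6 patients per cohort and schedule, with up to 12 at an expanded dose level. One unrecorded patient changes that cohort's TEAE rate by 1/3 = 33 percentage points, 1/6 = 17 points, or 1/12 = 8 points. This shows sensitivity only. It is not an estimate of how many events were missed.

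**The case against.** The strongest reply is that the rule is deliberate and the toxicity is reported elsewhere. Section 6.3.6 gives its own reason, that laboratory results are summarised in the CSR. Section 8.4.3 summarises haematology and chemistry by dose level cohort on the full analysis set, beside the TEAEs. DLTs have their own report, analysis set and summary. Interruptions and reductions are tabulated under 8.4.2. The Safety Review Team looks at all available safety data (6.8). All of this stands, and it limits the point. It does not remove it: the named outcome for the objective is TEAEs and SAEs, and a summary of laboratory values is not specified to carry causality or action taken. The DLT route covers only the first 21 or 28 days.

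Four stronger readings are tempting, and the protocol does not support them.

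- A reader might infer that these cytopenias categorically drop out of the TEAE outcome. The closing paragraph, the AE definition in 6.1 and the blood-dyscrasia example in Appendix A all give a site grounds to record them.
- A reader might infer that the MTD is compromised. DLTs are reported and analysed separately. Whether an afebrile, asymptomatic low count is a DLT at all is open to argument, because 7.2.2 excludes isolated laboratory changes without clinical significance.
- Section 6.7 says "Additional unscheduled PK samples should be collected for any AE" possibly related to AZD1775, so a reader might infer lost PK samples. Version 5 ends PK sampling on implementation, so this is not a consequence under the current version.
- A reader might apply an assumed event rate to the roughly 66 planned patients. The protocol gives no such rate, and the resulting count would require every site to record none of these events.

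It is also fair to say that amending 6.3.6 now has little prospective effect. Tables 2-4 are marked closed to enrolment, and after the FPV only SAEs, pregnancies and overdoses are collected.

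**Conclusion.** The contradiction is real and limited. For asymptomatic, non-serious deteriorations that do not end treatment, 6.3.6 gives two incompatible answers where dosing is reduced and no clear answer where it is only held or delayed. Under the main sentence, neutropenia or thrombocytopenia that triggers Table 9, Table 10 or the DLT limb for Grade 4 beyond 7 days would be missing from the TEAE tables. The size of any under-count cannot be derived from the document.

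The conclusion assumes that some sites follow the main sentence literally and that the investigator does not judge the event medically important. The damage is confined to the AE and TEAE record and the causality and action-taken data held with it. The primary DLT and MTD evaluation and the laboratory and exposure summaries are unaffected. The point deserves correction before lock, but it is not a threat to the study's main conclusion.

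**What to change.** Reconcile the two parts of 6.3.6 so that a protocol-mandated laboratory deterioration is recorded as an AE when it meets an SAE criterion, meets a DLT criterion, or leads to a hold, delay, reduction or discontinuation of AZD1775. Attach the closing examples to that rule. Keep the existing exception for unequivocal disease progression. This changes recording only and leaves every dosing and DLT rule as it is.

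Because enrolment is closed, apply the rule mainly to data already collected. Before database lock, list each hold, delay or reduction in the dosing record that coincides with a low neutrophil or platelet count, and query the site wherever there is no matching AE.

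The cost is one paragraph in the protocol and eCRF instructions and a short query round at about three centres. Reported haematologic TEAE rates will be slightly higher, and the CSR should say why.

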6.3.7 Hy's Law

Cases where a patient shows an AST or ALT $\geq 3xULN$, together with total bilirubin $\geq 2xULN$ may need to be reported as SAEs. Please refer to [Appendix D](#) for further instruction on cases of increases in liver biochemistry and evaluation of potential Hy's Law cases. Prompt reporting of cases meeting Hy's law criteria (via SAE expedited reporting system) is required for compliance with regulatory guidelines. The investigator is responsible for, without delay, determining whether a patient meets potential Hy's law (PHL) criteria.

6.3.8 Disease progression

Disease progression can be considered as a worsening of a patient's condition attributable to the disease for which the IP is being studied. It may be an increase in the severity of the disease

under study and/or increases in the symptoms of the disease. The development of new, or progression of existing metastasis to the primary cancer under study should be considered as disease progression and not an AE. Events which are unequivocally due to disease progression should not be reported as an AE during the study.

Events including diagnosis or signs and symptoms or the abnormal results of an investigation including those leading to hospitalization, which constitute or result from:

- a) ‘unequivocal progression’ (i.e., representative of overall disease status change, not a single lesion increase) of non-measurable/non-target disease,

or

- b) progression of malignancy under study (target disease) as determined per RECIST 1.1 criteria, should not be reported as AEs or SAEs.

Progression of the malignancy under study, including signs and symptoms of progression, should not be reported as a serious adverse events. Hospitalizations due to signs and symptoms of disease progression should not be reported as serious adverse events.

6.3.9 New cancers

The development of a new cancer should be regarded as an AE and will generally meet at least one of the serious AE criteria. New cancers are those that are not the primary reason for the administration of the study treatment and have been identified after the patient’s inclusion in this study. They do not include metastases of the original cancer.

6.3.10 Handling of deaths

All deaths that occur during the study or within the follow-up period after the administration of the last dose of study treatment must be reported as follows:

- Death which is unequivocally due to disease progression should be communicated to the study monitor at the next monitoring visit and should be documented in the eCRF module, but should not be reported as a SAE during the study.
- Where death is not clearly due to disease progression of the disease under study the AE causing the death should be reported by entering into the WBDC system as an SAE within 24 hours. The report should contain a comment regarding the co-involvement of progression of disease, if appropriate, and should assign a single primary cause of death together with any contributory causes.
- Death with an unknown cause should always be reported as a SAE but every effort should be made to establish a cause of death. A post-mortem may be helpful in the assessment of the cause of death, and if performed a copy of the post-mortem results (with translation of important parts into English) should be reported in an expedited fashion to an AstraZeneca representative within the usual timeframes.

6.4 Reporting of serious adverse events

All SAEs have to be reported, whether or not considered causally related to the AZD1775 or to the study procedure(s). All SAEs will be recorded in the eCRF. For patients continuing after the FPV (see Section 4.3.2.3), SAEs should be determined per protocol and must continue to be reported via the standard pharmacovigilance process (in paper) as stated below. For medical emergencies, refer to Section 6.4 below.

If any SAE occurs in the course of the study, then investigators or other site personnel inform appropriate AstraZeneca representatives immediately, or **no later than 24 hours** of when he or she becomes aware of it.

The designated Sarah Cannon representative works with the Investigator to ensure that all the necessary information is provided within 24 hours of investigator awareness.

For fatal or life-threatening adverse events where important or relevant information is missing, active follow-up is undertaken immediately. Investigators or other site personnel inform AstraZeneca representatives of any follow-up information on a previously reported SAE within one calendar day (i.e., immediately but no later than 24 hours) of when he or she becomes aware of it.

SAE information will be sent via secure e-mail connection or via fax. The Sarah Cannon Safety Department standard paper SAE Report with supporting relevant source documents (e.g. history and physical [H&P], hospital discharge summary, autopsy report when available, results of relevant diagnostic tests completed to evaluate the event) will be attached and sent via:

1. Secure email (Sarah Cannon SAE mailbox: [contact]) or by
2. Fax (Sarah Cannon safety fax number): [name]

Transmission of the SAE report Form should be confirmed by the site personnel submitting the report.

Follow-up information for SAEs and information on non-serious AEs that become serious should also be reported to Sarah Cannon Safety Department as soon as it is available; these reports should be submitted using the Sarah Cannon SAE Report Form. The detailed SAE reporting process will be provided to the sites in the SAE reporting guidelines contained in the study reference manual. The appointed study Medical Monitor works with the Investigator to ensure that all the necessary information is provided to the Sarah Cannon Safety Department **within 24 hours of investigator awareness**.

Investigators must report SAEs and follow-up information to their responsible IRB according to the policies of the responsible IRB. For fatal or life-threatening AEs where important or relevant information is missing, active follow-up is undertaken immediately.

AstraZeneca or their representative will provide Regulatory Authorities, Ethics Committees

(ECs), IRBs and PIs with clinical safety updates/reports according to local requirements.

Where appropriate, full details of the AE reporting process should be described in a Safety Handling Plan for the study.

